DEAKIN UNIVERSITY HUMAN RESEARCH ETHICS COMMITTEE PROJECT DESCRIPTION/PROTOCOL

Instructions for preparing the project description/protocol

- 1. The purpose of the Project Description is to provide the scientific and academic background and context of a research project.
- 2. A Project Description is a **mandatory** component of a submission using the Human Research Ethics Application (HREA).
- 3. The section headings in this Project Description template represent a structure for presentation of information about a research project that meets the needs of an ethics review body.
- 4. Not all headings or sub-headings in this template are relevant for each research project. Where a question is not relevant please enter NA into the response box. Please do not delete the question.
- 5. Researchers may use visual aids embedded in the project description/protocol to assist in describing their project where appropriate (e.g. images, videos etc.).
- 6. Submissions of clinical trial proposals may use alternative protocol templates, such as the SPIRIT statement.
- 7. Researchers may choose to submit an existing document (such as a protocol or project description that has already been developed) instead of developing a new document.
- 8. If researchers choose to submit an existing document instead of using one of the templates provided, they may need to provide indications to the ethics review body of where in the submitted document the content corresponding to the relevant fields in the template are located.
- 9. There is no need to duplicate information in the HREA into the Project Description or vice versa.
- 10. Language that is understandable to non-technical reviewers should be used.

COVID-19

All research must comply with current COVID-19 restrictions, as well as with Deakin's COVIDSafe Management Plan. Any activities considered as having high COVID-19 risk (e.g. requiring safety measures over and above the COVIDSafe Management Plan and risks covered by the general requirements of entry to campus) must have an approved COVIDSafe Activity Plan in place. This includes any on-campus research involving a face-to-face element, as well as off-site research (e.g., site visits, fieldwork etc).

1. Project details:

1.1 Please provide the project title - Dose response of alpha lactalbumin supplementation on serum TRP:LNAA ratio.

1.2 Please provide an acronym for the project (if appropriate) N/A

1.3 Please provide the project description/protocol version number N/A

2. Project Team Roles & Responsibilities:

2.1 Please provide the names, affiliations, positions and responsibilities of individuals involved in the project beyond those outlined in the HREA (e.g. technical or support staff).

Name: [name]

Affiliation: Centre for Sport Research, Deakin University

Position: Research Assistant

Responsibility: External researcher to provide participants with supplement to ensure double blinding

3. Resources:

3.1 Please provide details of the resources necessary for the project to be conducted, and the funding or support being sought or secured.

This project will be partially funded by an industry grant with Agropur US, who manufactures an alpha-lactalbumin protein supplement. In addition to providing complimentary supplement samples for the clinical trial, the additional funding provided by Agropur will cover the cost of meal provided to participants and the biochemical analysis of the blood samples. All questionnaires, diaries used in this study will incur no further cost for the project, as these subscriptions are provided by the University. Biochemical analysis will be completed in-house at Deakin University, with consumables such as venepuncture needles, vacutainers, and syringes to be purchased for this study.

The student researcher will perform biochemical and data analysis, which will incur no further cost to the project.

4. Background:

Please provide:

4.1 A lay summary of the literature review (approximately 1 A4 page)

Sleep, in humans, is defined as a complex reversible behavioural state where an individual is perceptually disengaged from and unresponsive to their environment(1). Sleep deprivation adversely affects several physiological mechanisms and can affect appetite, mood, alertness, glucose metabolism and protein synthesis (2).

Sleep is a dynamic process largely regulated by two factors: the circadian systems and the sleep homeostat. The homeostatic process is a function of sleep and waking, while the circadian process is controlled by a circadian oscillator(2). The circadian process is independent of sleep and waking and receives cues e.g. light from the environment. Core body temperature and melatonin rhythms are markers of this process. The suprachiasmatic nucleus (SCN) in the brain has melatonin receptor cells and as darkness falls melatonin is secreted by the pineal gland making the individual sleepy (3).

Tryptophan, an essential amino acid, acts as a precursor to Serotonin and Melatonin production and can influence the rate of synthesis and function of these neurotransmitters depending on its availability in the brain (1). Tryptophan is transported across the blood brain barrier by a system that shares transporters with several other large neutral amino acids (LNAA). Thus, it must compete with the other LNAAs to cross the blood brain barrier. The ratio of Tryptophan: LNAA can be increased

through consumption of tryptophan rich foods(4). Dietary sources of tryptophan include milk, turkey, chicken, fish, eggs, pumpkin seeds, beans, peanuts, cheese, and leafy green vegetables. However, the milk protein, alpha lactalbumin (ALAC) derived from whey has been reported as having the highest natural levels of tryptophan among all protein food sources (5).

It is hypothesized that nutrition interventions that act on altering the serum TRP:LNAA ratio levels could positively impact sleep (2). Dietary precursors such as ALAC have previously been found to increase the serum TRP:LNAA ratio by as much as 46 -130% and can further influence the rate of synthesis and function of neurotransmitters serotonin and melatonin(5, 6). Most of the existing literature surrounding ALAC and sleep is conducted amongst healthy trained participants or athletic population groups with regards to improving sleep efficiency (7-10). However, across these studies, varying doses ranging from 20 g to 60 g of alpha-lactalbumin (ALAC) were supplemented without clear indication of the rationale behind the dosage strategy. Additionally, while one study supplementing two separate 20 g ALAC doses at dinner meal and before bedtime found a positive outcome on morning after sleepiness (5); another study supplementing 20 g ALAC after morning exercise and 40 g ALAC before bedtime showed no significant difference in morning sleepiness measures (11). Hence, the specific effect of ALAC on

sleep architecture and the optimal timing of consumption has yet to be investigated and warrants further research.

Further, there exists no body of research surrounding the dose response effect of ALAC supplementation on serum TRP:LNAA ratio, independent of other factors such as glucose intake and carbohydrate rich poor protein (CRPP) diets. Literature suggests that the presence of other amino acids as well as glucose around the ALAC consumption can alter the serum TRP:LNAA ratio by further increasing the LNAA levels or by mechanisms such as insulin secretion that promotes the uptake of branched-chain amino acids into the muscle (1).

The proposed study aims to answer this question of identifying an optimal dose and time of evening alpha-lactalbumin (ALAC) supplementation to raise the serum TRP:LNAA ratio, without the influence of any other dietary factors such as glucose or other proteins.

4.2 A rationale/justification (i.e. how the research will fill any gaps, contribute to the field of research or contribute to existing or improved practice)

Tryptophan is a precursor of serotonin and melatonin, which are known to be involved in the regulation of various fundamental behavioural and physiological functions including sleep, wakefulness, circadian rhythms, cognition and even mood. Previous studies have reported that evening ALAC supplementation can effectively increase the TRP:LNAA ratio up to 130%. However, dose response studies for evening ALAC supplementation to identify the optimal dosage and time response to the ratio are yet to be explored.

Through this study we aim to be able to identify this optimal dosage of ALAC for further research and recommendations of this supplement in sleep and mood outcomes.

4.3 The research questions/aims/objectives/hypothesis

Research Question: What is the optimal dosage and timing of evening alpha-lactalbumin supplementation to increase the serum TRP:LNAA ratio?

Aim: To identify the optimal dosage of evening alpha-lactalbumin supplementation required to increase the serum TRP:LNAA ratio in healthy active population.

Objectives:

a) To study the dose response of 4 different doses i.e. 10, 20, 30, 40 g of ALAC supplementation on the TRP:LNAA ratio.

b) To observe the difference between the serum melatonin levels 3 hrs post consumption of 4 different ALAC dosages.

c) To test the palatability and appetite post 4 different dosages of ALAC supplementation.

Hypothesis:

1. There will be linear relationship between increasing ALAC dosages and serum TRP:LNAA ratio before reaching a plateau at ~40g.

2. Higher doses of ALAC will increase TRP:LNAA ratio for a longer time period

3. The palatability, appetite and preference will reduce at higher ALAC doses

4.4 The expected outcomes

The outcome of this study will be to identify the optimal dosage and timing of evening alphalactalbumin supplementation required to raise the serum TRP:LNAA ratio. This finding can be useful for further research on improving sleep outcomes with alpha-lactalbumin supplementation which requires the optimal TRP:LNAA ratio for its influence on sleep architecture.

5. Project Design:

Please provide details of:

The research project setting

5.1 This may include physical sites, online forums, and alternatives.

This research project will occur at the Deakin University Burwood campus, located in Burwood, Victoria, Australia. Participants will visit the testing laboratories of the Burwood campus, with testing to occur in this setting.

6. Methodology:

6.1 The methodological approach

A double blind crossover design has been selected. The double-blinded approach means both the researchers and participants will not know which dosage of the supplement is being received. Through a crossover design, each participant will receive all four dosages of the experimental supplement (α -lactalbumin), on four separate occasions, separated by a washout period of no lesser than 3 days (17, 18). As is the nature of a crossover trial, each participant will serve as their own control.

6.2 The rationale for choices of method/s (tied to project aims/objectives)

Double blinding ensures that both the research team and participants are unaware of the treatment dosages throughout the intervention, minimising the risk of bias. The crossover design allows for the participants to act as their own controls, thus limiting confounding influences of across subject variability. Assigning participants dosages via a latin square design model reduces the carryover effects from other within subject variables such as gender and other confounding variables and ensures proper balance such that the sequencing of experimental conditions does not affect outcomes of the trial.

7. The participants including:

7.1 A description and the number of participants

Sixteen participants (both genders i.e., male and female) will participate in the study.

7.2 The inclusion and exclusion criteria

Inclusions: Participants must be aged 18-35yrs, recreationally active i.e. completing at least 150 to 300 min moderate-intensity activity or 75–150 min of vigorous-intensity activity a week, plus muscle-strengthening activities 2 or more days a week (Tier 1 activity level) (12). *Exclusions:* Partipicants must not be facing any existing sleeping disorders such as insomnia or consuming any nutraceutical or herbal sleeping aids such as melatonin gummies, chamomile or other herbs which could influence exogenus melatonin production (13). Participants will be screened using the Pittsburgh Scale Quality Index (PSQI) questionnaire and a score of >5 will be excluded from the trial (14). Excessive beer or wine consumption (>17 standard drinks per week), dairy allergy, high caffeine use (e.g., >5 mg·kg-1·d-1), antidepressant or sleep medication use, current or recently finished night shift work (14), recent transmeridian travel, fluctuating bedtimes, and pregnancy are also exclusions from this trial due to confounding influences that may have on the circadian rhythm, exogenous melatonin production or the plasma TRP:LNAA ratio (15).

7.3 The sample size and statistical or power issues

Sixteen participants are to be recruited as per the statistical power analysis outlined in 11.4. This statistical power analysis was completed in consultation with a Deakin IPAN biostatistician and was performed using G-Power Analysis and Sample Size Software (Version 3.1).

7.4 Your participant recruitment strategies and timeframes (as required in addition to that outlined in the HREA)

[name] (student researcher) will be the primary researcher involved with recruitment. Participants will be recruited through flyers (Appendix 5) placed at Deakin University, local gym settings and sporting clubs, with online platforms (e.g., social media) also used to reach a wider audience. With permission from university unit chairs within the School of Exercise and Nutrition Sciences (see attached Organisation Consent Form), recruitment talks will be completed during lectures and classes within relevant units. Recruitment posts will be uploaded on CloudDeakin pages with permission from unit chairs. All interested individuals will be provided with a plain language statement (Appendix 6) and are to return a consent form to either [name] or [name]. No data collection will take place before written consent is received by the research team. Recruitment will commence in February 2024 (on approval of ethics) and will continue until a sample size of 16 individuals are recruited.

Before the first participant is recruited, this study will be registered within the ANZCTR

7.5 Your approach/es to provision of information to participants and/or consent (as required in addition to that outlined in the HREA)

Any interested individuals will be provided with a digital and hard copy of the plain language statement and consent form to keep (via REDCap). The plain language statement outlines the study design, contact details and states that an individual's decision to be involved in the study will not jeopardise their relationship with Deakin university and the research team. The consent form is to be signed and returned before any data collection is commenced.

7.6 If necessary, the type of consent provided to different participant groups, when and where, and any arrangements to confirm that consent

Written consent. All participants will be provided with a plain language statement and are to sign a consent form before participating in the trial.

7.7 If necessary, details of who will be confirming or re-negotiating consent with participants and the process/es that will be undertaken

Participants will be able to withdraw their consent at any time during the study which will not jeopardise their relationship with Deakin University. Participants must complete the 'withdrawal of consent form' (attached to the Plain Language Statement) and return it to a member of the research team.

8. Research Activities:

What you are going to do? Please include:

8.1 The participant commitment

Methods

Briefly, the screening phase will involve determination of study eligibility and will be administered via an online questionnaire. Upon selection post screening, each participant will be contacted to be explained the experimental protocol and to be scheduled to report to Deakin University (Burwood campus) on four separate occasions for the intervention separated by a washout period of no lesser than 3 days (17, 18).

Screening Session

To determine participant eligibility, participants will be screened, upon consent, using online questionnaire (Appendix 1) on REDCap to assess their eligibility for this study. The screening questionnaire will also involve questions around their training status to exclude any participants who are not recreationally active i.e., completing at least 150 to 300 min moderate-intensity activity or 75–150 min of vigorous-intensity activity a week, plus muscle-strengthening activities 2 or more days a week which classifies them as Tier 1 activity level. Sleep quality will be screened through the Pittsburgh Sleep Quality Index (Appendix 2) to exclude any participants with as PSQI score >5 as well as the presence of any pre-existing sleeping disorders such as insomnia will be screened at this stage.

Experimental Measures

Following screening, shortlisted participants with confirmed eligibility, will be contacted by the research team to explain the experimental protocol of the trial and to schedule their visits to the Deakin University Burwood Laboratory subsequently. At this point, participants will also be informed to complete a simple three day diet recall, prior to their first visit, using a smartphone app (Easy Diet Diary), to quantify the participants regular dietary intake, establish any dietary allergies and/or sensitivities, as well as, to ensure regular meal timings. This would help identify and eradicate any potential bias to the trial due to irregular meal patterns or extreme calorie restriction which could influence circardian cues and melatonin production (15).

Randomisation

Participants will be randomly allocated a single dose of the α -lactalbumin (BiPRO Alpha 9000; Agropur Inc, Appleton, WI), in a crossover design (each participant will complete all 4 doses on 4 different occasions) on their scheduled lab visit dates. A latin square design will be used for a counterbalanced randomisation of the dosages to the participants to avoid any potential carryover effects or within participant variability. To blind both participants and the research team, the experimental drinks will be matched for taste and provided to the participants by an external researcher. The latin square model will ensure adequate sequencing of the dosages across at the participants to avoid within subject variability.

Intervention

Participants will be required to report to the university at 17:00 hrs with a fasting period 2.5 hrs before arrival (14:30 hrs). Upon their arrival, simple height and weight measures will be taken by the researchers. Within the first hour of arrival, a trained researcher will insert a cannula into a forearm vein of the participants for blood samples to be taken. Baseline blood and saliva samples will be collected before the experimental supplement consumption. Further, each participant will be provided the experimental ALAC protein shake and a Visual Analog Scale (VAS) -sensory evaluation questionnaire to assess the preference of the ALAC shake at immediately post consumption of the drink (T=0 mins). Participants will also complete a Visual Analog Scale VAS -GI symptoms questionnaire, at two time points i.e. baseline (T=0 mins) and 2hrs post supplement consumption i.e. (T= 120 mins). Small amounts of blood will be drawn (5 mL) at half an hour interval from the time of the supplement consumption (pre supplement and 90 mins, 120 mins, 180 mins and 210 mins post supplement). During the experimental protocol, from T=0 to T= 210 mins, the participants will be asked to relax in an environment consistent lighting and discouraged from using screens. A saliva swab collection will once again be repeated at 3 hrs (210 mins) post supplement consumption. A simple chronotype questionnaire will also be administered to all the participants at this stage. At the end of the study protocol i.e., **21:00hrs**, the participants will be screened for alertness via Karolinska Sleepiness Scale (KSS)(Appendix 4) to assess their ability to drive back home post the intervention and in the event a participant scores >6.8 on the KSS scale, alternate arrangements to travel back home or temporary sleeping arrangements at Deakin University Campus will be made to ensure the participant's safety. Participants will also be handed a boxed dinner meal before leaving the lab. This procedure will be replicated for each of the four visits made be every participant, during the intervention. Participants will also receive a reimbursement via \$100 gift card on successfully completing all 4 intervention sessions.

Wash-out

The wash-out phase is defined as a period of minimum three days to limit any carry-over effect of the ALAC supplement on the serum Tryptophan:LNAA ratio before administering the next dose. This ensures that the experimental protein dosages are adequately separated. This period is defined based on previous literature which has observed that a gap of 1-3 days to be sufficient to reverse the effect of a single dose of tryptophan on TRP:LNAA ratio (17,18). During the wash-out period, the participants will be required to continue eating and training as per their usual routine. No supplement will be provided during this phase.

DAY	DOSE 1	WASHOUT			DOSE 2	WASHOUT			DOSE 3	WASHOUT			DOSE 4
		2	3	4	5	6	7	8	9	10	11	12	13
17:00	(i) E												
17:15 BASELINE	۱.				♦ Ĥ				♦ Ĥ				۲
17:30 SH	É				∲ ₿				€ġ				1
					٢				٢				۲
19:30 Ŭ	• 🖻				\\$				\\$				•[
20:00	٢				٢				٢				۲
20:30	 ♦ ∯ 								۱.				٢
	FE PN				E M				E D				SE J

Figure 1 -Graphical description of the study protocol. Example of a participant prescribed all 4 doses of alpha -lactalbumin supplement in random order and the measures taken at different time intervals.

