11.1 How will you measure, manipulate and/or analyse the information that you collect/gather?

Initially, data cleaning will be performed to identify missing and corrupt data. Data will be analysed using generalised linear mixed models within StataIC 16 (StataCorp LLC, TX, USA). The effect of dietary intervention (dose response effect of α -lactalbumin) and time period (i.e., sequence receiving condition) and their interaction, will be fitted as fixed effects to determine whether there was a difference in the effect of dietary intervention over period on dependant variables of amino acid analysis and plasma melatonin. Participant identification number will be used as a random factor to account for repeated measures in each model.

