11.2 Please describe your matching and sampling strategies

There will be no requirement to create matched groups due to the repeated measures study design. Each participant will act as their own control.

11.3 Please outline how you will account for potential bias, confounding factors and missing information

Bias

- Double-blinded study

-The different α -lactal bumin dosages to be matched for taste. An external researcher is to provide participants with the supplement to ensure the research team remains blinded to the experimental dosage.

- Diet – As protein and carbohydrates can influence the TRP:LNAA ratio, participants will be asked to come in fasting for a period of 3 hrs before the alpha-lactalbumin supplement consumption.

- Light will be controlled for after the supplement consumption and screen usage or viewing will be restricted to limit the impact of light on endogenous melatonin levels

Missing values will not be substituted in any circumstance (missing or otherwise). There are no planned data cleaning processes, with raw values only to be analysed.

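### The model in Protocol 11.1 uses neither the visit's pre-supplement ratio nor sampling time, which costs precision; and 11.1 and 11.3 contradict each other on data cleaning

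*Protocol*

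**What the plan says.** **Sampling.** Protocol 8.1 (Intervention) states that "Baseline blood and saliva samples will be collected before the experimental supplement consumption". Blood is drawn at five times: "pre supplement and 90 mins, 120 mins, 180 mins and 210 mins post supplement". "This procedure will be replicated for each of the four visits", so each participant has a visit-specific starting value at every dose.

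**Model.** Protocol 11.1 fits the dose effect and "time period (i.e., sequence receiving condition) and their interaction, will be fitted as fixed effects", with participant as the random factor. Neither a baseline value nor the time of the blood draw is listed. The time factor is defined as the order in which conditions are received, so it is the crossover period and not minutes after the drink.

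**Food.** The aim in 4.1 is to study the supplement "without the influence of any other dietary factors such as glucose or other proteins". Section 11.3 accepts that protein and carbohydrate affect the ratio. The control on the test day is a fast from 14:30, about 3 h before the 17:30 drink. No meal is standardised, usual eating continues between visits, and participants "complete a simple three day diet recall, prior to their first visit", with no later record.

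**Cleaning.** Section 11.1: "Initially, data cleaning will be performed to identify missing and corrupt data". Section 11.3: "There are no planned data cleaning processes, with raw values only to be analysed".

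**The concern.** A random participant effect removes stable differences between people. It does not remove a participant's differences in starting ratio from one visit to the next. What was eaten before 14:30 can differ across the four visits, and the pre-supplement sample is the measurement that captures what is left of it. As written, the model does not use that information, although the blood is already drawn. With 16 participants, residual noise matters.

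The missing sampling-time term raises a second problem. Five samples per visit are taken, and 11.1 does not say which are outcomes. If all five enter as outcome rows, one of them cannot carry a dose effect.

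The cleaning conflict is a separate matter. An analyst who meets a failed or implausible assay value has two opposing instructions, and the choice could be made after results are seen.

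**Working it through.** The plan gives no figure for baseline adjustment to reproduce. The nearest is the power statement in 11.4, which is taken up in step 4.

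**1. Gain from the covariate.** Let r be the correlation between pre- and post-dose ratio within a visit, after the participant effect. The documents do not give r; 0 to 0.7 is assumed. The variance of a dose contrast is multiplied by 1 − r², and the equivalent sample size is 16/(1 − r²).

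| r (assumed) | 1 − r² | Variance removed | Equivalent n |
|---|---|---|---|
| 0 | 1.00 | 0% | 16 |
| 0.3 | 0.91 | 9% | 17.6 |
| 0.5 | 0.75 | 25% | 21.3 |
| 0.7 | 0.51 | 49% | 31.4 |

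A change score instead multiplies the variance by 2(1 − r): 2.0, 1.4, 1.0 and 0.6. It loses precision whenever r is below 0.5, so the covariate is the better choice.

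**2. Bias or noise?** A 4×4 Williams square with 16 participants was simulated (4000 runs), with a shared visit component in the pre- and post-dose values and a true largest contrast of 0.024. The unadjusted, baseline-adjusted and change-score models all averaged about 0.024. Standard errors, unadjusted against adjusted:

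- Shared fraction 0.3: 0.0176 and 0.0170; (0.0170/0.0176)² = 0.93, so 7% less variance.
- Shared fraction 0.5: 0.0174 and 0.0153; ratio squared 0.77, so 23% less.
- Shared fraction 0.7: 0.0177 and 0.0129; ratio squared 0.53, so 47% less.

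The gains are slightly below the formula's.

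**3. Pre-dose row as an outcome.** If all five samples are outcome rows with no sampling-time term, the dose contrast averages four post-dose rows and one row whose expected dose effect is zero. With complete data it is 4/5 of the mean post-dose contrast; a post-dose difference of 0.024 would appear as 0.8 × 0.024 = 0.0192. This applies only under that reading of 11.1.

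**4. Effect on power.** Inputs from 11.4: n = 16, difference 0.024, root within mean square error 0.05, alpha 0.01. Sidedness is not stated; two-sided is taken.

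- SD of the difference 0.05: standardised difference 0.024/0.05 = 0.48, power 19.4%, not the stated 85%. With the covariate: 19.0% (r = 0), 21.3% (0.3), 26.9% (0.5), 42.0% (0.7).
- SD of the difference √2 × 0.05 = 0.0707: standardised difference 0.34, power 8.7%. With the covariate: 11.8% (r = 0.5), 18.6% (0.7).

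The failure of 85% to reproduce is a separate matter for 11.4. Adjustment helps but does not close that gap.

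**5. Cleaning rules side by side.** Section 11.1 makes cleaning the first step and gives its purpose as finding missing and corrupt data. Section 11.3 says that no cleaning process is planned. No ordering of steps satisfies both.

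**The case against.** The strongest reply is that the design already deals with food. Every participant takes every dose, dose order is randomised by a counterbalanced Latin square, and the fast limits what a meal can contribute. This stands as far as bias goes. A reader might infer that unstandardised lunches distort the dose comparison; the design does not support that, and the simulation shows no bias. Only precision is lost.

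A reader might also infer that the raw-values sentence in 11.3 forbids baseline adjustment. It does not: it follows the rule on missing values and concerns cleaning and imputation, and a pre-supplement value used as a covariate is still a raw value.

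Nor can it be said that pre-dose melatonin is measured and then ignored. Objective b in 4.3 names only 3 h after the drink, 9.2 does not say which plasma samples are assayed, and no analyte is named for saliva. The point is firm for the ratio only.

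The size of the gain is open. Post-dose samples come 90 to 210 minutes after a 10 to 40 g protein load, so r could be near zero; adjustment would then gain nothing and cost a degree of freedom.

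Finally, covariates and assay limits are often left to an analysis plan. That holds for details such as transformation. Here, however, the protocol states a model and states two cleaning rules, and those statements are what needs correcting. On cleaning, 11.1 speaks of identifying corrupt data and does not say that they would be deleted; the conflict is over whether cleaning happens at all.

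**Conclusion.** The point holds as a matter of precision and of clear specification. The protocol collects a visit-specific starting ratio, and its stated model has no term for it or for sampling time. The loss is between nothing and about half of the contrast variance over r from 0 to 0.7, a range that is assumed. If the pre-dose sample were also treated as an outcome, the dose effect would be diluted by a fifth with complete data; the text leaves this open and does not say that it will happen. The contradiction between 11.1 and 11.3 on cleaning is certain and rests on no assumption. These points should be fixed before the dose code is opened. They do not undermine the design.

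**What to change.** **In 11.1:**
- State that the post-dose samples are the outcome. This must come first; otherwise the same pre-dose value could stand on both sides of the model.
- Add sampling time and dose by sampling time. Hypothesis 2 in 4.3, on how long the ratio stays raised, needs the interaction in any case.
- Fit the visit's pre-supplement ratio as a covariate, ideally split into the participant's mean and the visit's deviation from it, so that between- and within-participant slopes are not blended.
- Do the same for melatonin only if a pre-dose melatonin value is assayed, and say whether it is.

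**In 11.3:** replace the sentence that rules out cleaning with one that agrees with 11.1, for example: failed or implausible assay values are flagged by limits written before the dose code is opened, and nothing is imputed.

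**Cost:** wording, about one degree of freedom for the covariate (two if it is split), those for the sampling-time terms, and no additional blood samples for the ratio. Asking participants to repeat and log the same lunch at each visit is an optional design preference with a small burden; the analysis fix does not depend on it.
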